#### 12.2.2 Displays of Adverse Events

Clinical AEs	Mild (Grade 1)	Moderate (Grade 2)	Severe (Grade 3)				
CARDIOVASCULAR							
Arrhythmia		Asymptomatic or transient signs; no medical intervention required.	Recurrent and/or persistent signs; symptomatic medical intervention required.				
Hemorrhage	Estimated blood loss 100 mL .	Estimated blood loss >100 mL; no transfusion required.	Blood transfusion required.				
RESPIRATORY							
Cough	Transient cough; no treatment required.	nt cough; no treatment Persistent cough; treatment Int required.					
Bronchospasm, Acute	Transient bronchospasm; no treatment required; FEV1 71-80% of predicted peak flow.	Requires treatment; normalizes with bronchodilator; FEV1 60-70% of predicted peak flow.	No normalization with bronchodilator; FEV1 <60% of predicted peak flow.				
Dyspnea	Does not interfere with usual and social activities.	Interferes with usual and social activities; no treatment.	Prevents usual and social activities OR requires treatment.				
EAR AND LABYRINTH	DISORDERS						
Hearing Impairment (Adult enrolled on a Monitoring Program (on a 1, 2, 4, 3, 6, and 8 kHz audiogram)	npairmentolled on ag Program (on, 6, and 8 kHzThreshold shift of 15 - 25 dBaveraged at 2 contiguous testfrequencies in at least one ear.Threshold shift of >25 dBaveraged at 2 contiguous testat least one ear.		Threshold shift of >25 dB averaged at 3 contiguous test frequencies in at least one ear; therapeutic intervention indicated.				
Tinnitus	Mild symptoms; intervention not indicated.	Moderate symptoms; limiting instrumental ADL.	Severe symptoms; limiting self-care ADL.				
Vertigo	Mild symptoms.	Moderate symptoms; limiting instrumental ADL.	Severe symptoms; limiting self-care ADL.				
GASTROINTESTINAL							
Nausea	No interference with normal activity.	Some interference with normal activity.	Prevents daily activities.				
Vomiting	No interference with activity OR 1-2 episodes in a 24-h period.	Some interference with activity OR >2 episodes in a 24-h period.	Prevents daily activity OR requires medical intervention.				
Diarrhea	2-3 loose or watery stools in a 24- h period.	4-5 loose OR watery stools in a 24- h period. 6 or more loose or wate 24-h period OR requires OR requires medical in					
Oral Discomfort / Dysphagia	Mild discomfort; no difficulty swallowing.	Some limits on eating /drinking.	Eating/talking very limited; unable to swallow solid foods.				

#### Table 3: Clinical Adverse Event Toxicity Grading Scales

#### 12.2.2 Displays of Adverse Events

Clinical AEs	Mild (Grade 1)	Moderate (Grade 2)	Severe (Grade 3)								
LOCAL IV CATHETER	REACTION										
IV site reaction	Not applicable.	Erythema with associated symptoms (e.g., edema, pain, induration, phlebitis).	Ulceration or necrosis; severe tissue damage; operative intervention indicated.								
SYSTEMIC REACTION	S										
Anaphylaxis **			Symptomatic bronchospasm, with or without urticaria; parenteral intervention indicated; allergy-related edema or angioedema; hypotension.								
** Definition : A disorder characterized by an acute inflammatory reaction resulting from the release of histamine and histamine-like substan from mast cells, causing a hypersensitivity immune response. Clinically, it presents with breathing difficulty, dizziness, hypotension, cyanosis and loss of consciousness, and may lead to death.											
Allergic Reaction	Pruritus without rash.	Localized urticaria OR requires oral therapy.	Generalized urticaria OR angioedema OR anaphylaxis OR requires epinephrine								
Hypersensitivity (including drug fever) Transient flushing or rash; temperature 38.0-38.4°C (100.4- 101.1°F).		Rash; flushing; urticaria; dyspnea; temperature 38.5 - 38.9°C (101.2 – 102.0°F).	Symptomatic bronchospasm with or without urticaria; parenteral medication indicated; allergy-related edema or angioedema; hypotension; temperature >38.9°C (>102.0°F).								
Headache	No interference with activity.	Repeated use of non-narcotic pain reliever for more than 24 h OR some interference with activity.	Significant; any use of narcotic pain reliever OR prevents daily activity OR requires triptans.								
Fatigue	No interference with activity.	Some interference with activity.	Significant; prevents daily activity.								
Myalgia	No interference with activity.	Some interference with activity.	Significant; prevents daily activity.								
SKIN											
Mucocutaneous	Erythema, pruritus.	Diffuse, maculo-papular rash, dry desquamation.	Vesiculation OR moist desquamation OR ulceration.								
Pruritus	No or minimal interference with usual social and functional activities.	Greater than minimal interference with usual social and functional activities.	Inability to perform usual social and functional daily activities.								

#### Table 3: Clinical Adverse Event Toxicity Grading Scales (Continued)

#### 12.2.2 Displays of Adverse Events

### Table 3: Clinical Adverse Event Toxicity Grading Scales (Continued)

Clinical AEs	Mild (Grade 1)	Moderate (Grade 2)	Severe (Grade 3)
ALL OTHER CONDITIO	DNS		
Illness or clinical AE (as defined according to applicable regulations)	Require minimal or no treatment; does not interfere with the participant's daily activities.	Result in a low level of inconvenience or concern with therapeutic measures; may cause some interference with functioning.	Interrupt a participant's usual daily activity and may require systemic drug therapy or other treatment; are usually incapacitating.

#### 12.4.1 Individual Laboratory Measurements and Abnormal Laboratory Values

#### Table 4: Clinical Laboratory Reference Ranges and Toxicity Grading Scales

Laboratory AEs	Reference Ranges	Mild (Grade 1)	Moderate (Grade 2)	Severe (Grade 3)
Blood, serum, or plasma	Ranges	(Grade I)	(Grade 2)	(Grade b)
HEMATOLOGY				
Hemoglobin decrease, female – g/dL	11.1 – 15.9	9.6 - 11.0	8.0 - 9.5	<8.0
Hemoglobin decrease. male – g/dL	13.0 - 17.7	11.0 - 12.9	8.5 - 10.9	<8.5
WBC increase $- x10^3 / \mu L$	3.4 - 10.8	>10.8 - 15.0	>15.0 - 20.0	>20.0
WBC decrease $-x10^3/\mu L$	3.4 - 10.8	2.4 - <3.4	1.4 - <2.4	<1.4
Neutrophils decrease $- x 10^{3/} \mu L$	1.4 - 7.0	1.0-<1.4	0.75 - <1.0	< 0.75
Lymphocytes decrease $-x10^3/\mu L$	0.7 - 3.1	<0.7 -0.4	<0.4 - 0.3	<0.30
Monocytes increase $-x10^3/\mu L$	0.1 - 0.9	>0.9 - 2.0	>2.0 - 3.0	>3.0
Eosinophils increase $- x 10^3 / \mu L$	0.0 - 0.4	>0.4 - 0.75	>0.75 - 1.0	>1.0
Basophils increase $- x10^{3}/\mu L$	0.0-0.2	>0.2 - 0.5	>0.5-0.8	>0.8
Platelets decrease $- x 10^3 / \mu L$	150 - 450	90 - <150	55 - <90	<55
COAGULATION				
PT INR	0.9 - 1.2	>1.2-1.8	>1.8-2.1	>2.1
Prothrombin Time	9.1 - 12.0	>12.0-15.0	>15.0-18.6	>18.6
Activated Partial Thromboplastin Time (APTT)	24 - 33	>33.0-54.0	>54.0-75.0	>75.0
CHEMISTRY		I		
Sodium decrease – mmol/L	134 - 144	130 - 133	124 –129	<124
Sodium increase – mmol/L	134 - 144	145 - 150	151 – 156	>156
Potassium increase – mmol/L	3.5 - 5.2	5.3 - 6.0	6.1 - 6.5	>6.5
Potassium decrease – mmol/L	3.5 - 5.2	3.4-3.2	2.5 - 2.9	<2.5
Total Carbon Dioxide (CO 2 ) increase – mmol/L	20 - 29	30 - 35	36 - 37	>37
Total Carbon Dioxide (CO2) decrease – mmol/L	20-29	17 - 19	14 - 16	<14
Calcium decrease – mg/dL	8.7 - 10.2	7.8 - 8.6	7.0 - 7.7	<7.0
Calcium increase – mg/dL	8.7 - 10.2	10.3 - 11.4	11.5 - 12.5	>12.5
Magnesium decrease – mg/dL	1.6 - 2.3	1.2 - 1.5	1.1 - 0.9	<0.9
Blood urea nitrogen (BUN) increase, 18-39Y - mg/dL	6-20	21 - 58	59-120	>120
Blood urea nitrogen (BUN) increase, 40-59Y – mg/dL	6-24	25 - 58	59 - 120	>120
Glucose decrease, fasting – mg/dL	65 – 99	47 - 64	42 - 46	<42
Glucose increase, fasting – mg/dL	65 – 99	100 - 160	161 - 250	>250
Creatinine increase, male – mg/dL	0.76 - 1.27	1.28 - 1.90	1.91 - 3.80	>3.80
Creatinine increase, female – mg/dL	0.57 - 1.00	0.58 - 1.50	1.51 - 3.00	>3.00
Direct bilirubin	0.0 - 0.40	0.41 - 0.70	0.71 - 1.20	>1.20
Total bilirubin (serum) increase – mg/dL (with other LFTs in the normal range)	0.0 - 1.2	1.3 - 2.0	2.1 - 2.5	>2.5
Total bilirubin (serum) increase – mg/dL (accompanied by a >3 x ULN increase in ALT or AST)	0.0 - 1.2	1.3 – 1.7	1.8 - 2.4	>2.4
Total protein decrease – g/dL	6.0 - 8.5	5.1 - 5.9	4.6-5.0	<4.6
Albumin, decrease, Male, 18-30Y - g/dL	4.1 - 5.2	4.0 - 3.5	2.0-2.9	<2.0

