Pruritus	No or minimal interference with usual social and functional activities.	Greater than minimal interference with usual social and functional activities.	Inability to perform usual social and functional daily activities.			
ALL OTHER CONDITIONS						
Illness or clinical AE (as defined according to applicable regulations)	Require minimal or no treatment; does not interfere with the subject's daily activities.	Result in a low level of inconvenience or concern with therapeutic measures; may cause some interference with functioning.	Interrupt a subject's usual daily activity and may require systemic drug therapy or other treatment; are usually incapacitating.			

Table 3:	Toxicity	Grading	Tables –	LABOR	ATORY AE
1 4010 01	1 Onicity	Ol wanning	1 460105		II OILI IID.

	Mild	Moderate	Severe
Laboratory AEs	(Grade 1)	(Grade 2)	(Grade 3)
Blood, serum, or plasma	*		
HEMATOLOGY			
Hemoglobin decrease, female – g/dL	9.6 – 11.0	8.0 - 9.5	<8.0
Hemoglobin decrease, male – g/dL	11.0 - 12.9	8.5 - 10.9	<8.5
WBC increase $- x10^3/ \mu L$	>10.8 - 15.0	>15.0-20.0	>20.0
WBC decrease – $x10^{3/} \mu L$	2.4 - <3.4	1.4 - < 2.4	<1.4
Neutrophils decrease – $x10^{3/} \mu L$	1.0 - < 1.4	0.75 - < 1.0	<0.75
Lymphocytes decrease – $x10^{3/} \mu L$	<0.7 –0.4	< 0.4 - 0.3	<0.30
Monocytes increase – $x10^{3/} \mu L$	>0.9 - 2.0	>2.0 - 3.0	>3.0
Eosinophils increase – $x10^{3/} \mu L$	>0.4-0.75	>0.75 - 1.0	>1.0
Basophils increase – $x10^{3/} \mu L$	>0.2-0.5	>0.5 - 0.8	>0.8
Platelets decrease $- x 10^3 / \mu L$	90 - <150	55 - <90	<55
COAGULATION			
PT INR ratio	>1.2 - 1.8	>1.8 - 2.1	>2.1
Prothrombin Time (PT) - seconds	>12.0 - 15.0	>15.0-18.6	>18.6
Activated Partial Thromboplastin Time (APTT) - seconds	>33.0 - 54.0	>54.0 - 75.0	>75.0
CHEMISTRY			
Sodium decrease – mmol/L	130 - 133	124 – 129	<124
Sodium increase – mmol/L	145 - 150	151 - 156	>156
Potassium increase – mmol/L	5.3 - 6.0	6.1 - 6.5	>6.5
Potassium decrease – mmol/L	3.4-3.0	2.5 - 2.9	<2.5
Total Carbon Dioxide (CO 2 ) increase – mmol/L	30 - 35	36 - 37	>37
Total Carbon Dioxide (CO 2 ) decrease – mmol/L	17 - 19	14 - 16	<14
Calcium decrease – mg/dL	7.8-8.6	7.0 - 7.7	<7.0
Calcium increase - mg/dL	10.3 - 11.4	11.5 – 12.5	>12.5
Magnesium decrease – mg/dL	1.2 - 1.5	1.1 - 0.9	<0.9

Laboratory AEs	Mild (Grade 1)	Moderate (Grade 2)	Severe (Grade 3)
Blood urea nitrogen (BUN) increase, 18-39Y - mg/dL	21 - 58	59 – 120	>120
Blood urea nitrogen (BUN) increase, 40-59Y – mg/dL	25 - 58	59 – 120	>120

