Glucose decrease, fasting – mg/dL	55 - 69	40 - 54	<40
Glucose increase, fasting – mg/dL	100 - 160	161 - 250	>250
Creatinine increase, male – mg/dL	1.28 - 1.90	1.91 - 3.80	>3.80
Creatinine increase, female – mg/dL	0.58 – 1.50	1.51 - 3.00	>3.00
Direct bilirubin	0.41 - 0.70	0.71 - 1.20	>1.20
Total bilirubin (serum) increase – mg/dL (with other LFTs in the normal range)	1.3 – 2.0	2.1 - 2.5	>2.5
Total bilirubin (serum) increase – mg/dL (accompanied by a >3 x ULN increase in ALT or AST)	1.3 – 1.7	1.8 - 2.4	>2.4
Total protein decrease – g/dL	5.1 – 5.9	4.6 - 5.0	<4.6
Albumin, decrease, Male, 18-30Y - g/dL	4.0 - 3.0	2.0-2.9	<2.0
Albumin decrease, Female, 18-30Y – g/dL	3.8 - 3.0	2.0–2.9	<2.0
Albumin decrease, Male, 31-50Y – g/dL	3.9 - 3.0	2.0-2.9	<2.0
Albumin decrease, Female, 31-50Y – g/dL	3.7 – 3.0	2.0–2.9	<2.0
AST increase – U/L	41 - 80	81 - 120	>120
ALT increase, male – U/L	45-88	89 - 132	>132
ALT increase, female – U/L	33 - 64	65 – 96	>96
Alkaline phosphatase (AP) increase, males 18-20Y – U/L	126 - 250	251 - 375	>375
Alkaline phosphatase (AP) increase, females, 18-20Y – U/L	107 – 250	251 - 375	>375
Alkaline phosphatase (AP) increase, 21-150Y – U/L	122 – 250	251 - 375	>375

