#### Table 3: Toxicity Grading Tables – LABORATORY AEs
Laboratory AEs	Mild (Grade 1)	Moderate (Grade 2)	Severe (Grade 3)					
Urine								
URINALYSIS by Dipstick								
Protein	1+	2+	>2+					
Blood (occult)	1+	2+	>2+					
Glucose	1+	2+	>2+					
URINE MICROSCOPY								
Red blood cells (RBC) per HPF	3-10	11-30	>30 and/or gross blood					
White blood cells (WBC) per HPF	6-10	11-30	>30 and/or symptomatic urogenital infection					
Bacteria (microscopic)	few	moderate many						

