#### **12.4.1** Individual Laboratory Measurements and Abnormal Laboratory Values

#### Table 4: Clinical Laboratory Reference Ranges and Toxicity Grading Scales (Continued)

Laboratory AEs	Reference Ranges	Mild (Grade 1)	Moderate (Grade 2)	Severe (Grade 3)			
Albumin decrease, Female, 18-30Y - g/dL	3.9 - 5.0	3.8 - 3.5	2.0-2.9	<2.0			
Albumin decrease, Male, 31-50Y – g/dL	4.0 - 5.0	3.9 - 3.5	2.0-2.9	<2.0			
Albumin decrease, Female, 31-50Y – g/dL	3.8 - 4.8	3.7 – 3.5	2.0-2.9	<2.0			
AST increase – U/L	0-40	41 - 80	81 - 120	>120			
ALT increase, male – U/L	0-44	45-88	89 - 132	>132			
ALT increase, female – U/L	0 - 32	33 - 64	65 - 96	>96			
Alkaline phosphatase (AP) increase, males 18-20Y - U/L	51 - 125	126 - 250	251 - 375	>375			
Alkaline phosphatase (AP) increase, females, 18-20Y - U/L	42 - 106	107 - 250	251 - 375	>375			
Alkaline phosphatase (AP) increase, 21-150Y – U/L	44 - 121	122 - 250	251 - 375	>375			
Urine							
URINALYSIS by Dipstick							
Protein	negative / trace	1+	2+	>2+			
Blood (occult)	negative	1+	2+	>2+			
Glucose	negative	1+	2+	>2+			
URINE MICROSCOPY							
Red blood cells (RBC) per HPF	0 - 2	6-10	11-50	>50 and/or gross blood			
WBC (microscopic) – WBC per HPF	0 - 5	6-10	11-50	>50			
Bacteria (microscopic)	none / few	few	moderate	many			
Note 1: With the exception of AST ALT AP bilightin electrolytes urine protein BUN and creatining which should be within reference							

Note 1: With the exception of AST, ALT, AP, bilirubin, electrolytes, urine protein, BUN and creatinine, which should be within reference range, lab values of other analytes in the grade 1 range are acceptable for enrollment if (a) they are not considered to be clinically significant by the investigator and (b) there is no cluster of abnormal labs that combined are suggestive of an underlying disorder.

Note 2: Other Exceptions to screening laboratory tests' normal reference ranges are:

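### SAP Table 4 and protocol Appendix B Table 3 grade five laboratory analytes with different cut-offs, and SAP Table 4 leaves some out-of-range values without a grade

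*SAP*

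**What the plan says.** Protocol section 9.2.3 assesses post-dose laboratory abnormalities with the Appendix B scales, and any abnormality of Grade 1 or higher in Table 3 of that appendix is entered as a TEAE. SAP sections 4.5.1 and 9.6 grade the same results with SAP Table 4, which feeds the severity displays (Tables 29–30 for chemistry, Tables 47–48 for urinalysis).

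Four of the five differing rows, SAP first and then protocol. The SAP rows start with a reference range; the protocol rows do not.

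- Glucose decrease: "Glucose decrease, fasting – mg/dL 65 – 99 47 - 64 42 - 46 <42" against "Glucose decrease, fasting – mg/dL 55 - 69 40 - 54 <40".
- Potassium decrease: "Potassium decrease – mmol/L 3.5 - 5.2 3.4-3.2 2.5 - 2.9" against "Potassium decrease – mmol/L 3.4-3.0 2.5 - 2.9".
- Albumin decrease, one of four strata: "Albumin decrease, Female, 18-30Y - g/dL 3.9 - 5.0 3.8 - 3.5 2.0-2.9" against "Albumin decrease, Female, 18-30Y – g/dL 3.8 - 3.0".
- Urine RBC: "Red blood cells (RBC) per HPF 0 - 2 6-10 11-50" against "Red blood cells (RBC) per HPF 3-10 11-30".

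The fifth is urine WBC. Grade 2 runs 11–50 per HPF in the SAP and 11–30 in the protocol, and protocol Grade 3 also includes symptomatic urogenital infection, which the SAP omits.

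Both documents say that a Grade 1 value present before dosing counts as treatment-emergent only if it rises to Grade 2 or higher. The SAP is version 1.0 of 7 February 2023 and cites protocol v3.0 in several places (for example sections 4.3 and 4.5.1). The protocol under review is version 5.0 of 10 July 2023.

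**The concern.** One set of results would be graded by two rulers in one clinical study report. The TEAE tables follow the protocol's grades and the laboratory severity tables follow the SAP's, so a reader comparing them would find the same measurement at different severities with no explanation.

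The gaps are a separate problem inside the SAP. A potassium of 3.2 is Grade 1, 3.1 has no grade, and 2.9 is Grade 2. Albumin behaves the same way between 3.5 and 2.9. A result can worsen and drop out of the severity rows. Changes in clinical laboratory parameters are a secondary endpoint, and the SMC reviews both TEAEs and laboratory results after Cohort T4.

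**Working it through.** **Method.** Take each reportable value, read its grade from each table, and list every value where the two differ. The steps are 1 mg/dL for glucose, 0.1 for potassium and albumin, and 1 cell per HPF for urine microscopy. The protocol cut-offs come from Appendix B Table 3 and the SAP cut-offs from Table 4. The plan states no figure of its own to reproduce.

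| Analyte | Protocol G1 / G2 / G3 | SAP reference; G1 / G2 / G3 | Values that differ (protocol → SAP) |
|---|---|---|---|
| Glucose decrease, mg/dL | 55–69 / 40–54 / <40 | 65–99; 47–64 / 42–46 / <42 | 40–41 (2 → 3); 47–54 (2 → 1); 65–69 (1 → within reference) |
| Potassium decrease, mmol/L | 3.0–3.4 / 2.5–2.9 / <2.5 | 3.5–5.2; 3.2–3.4 / 2.5–2.9 / <2.5 | 3.0–3.1 (1 → none) |
| Albumin decrease, g/dL, each stratum | G1 floor 3.0; 2.0–2.9; <2.0 | G1 floor 3.5; 2.0–2.9; <2.0 | 3.0–3.4 (1 → none) |
| Urine RBC per HPF | 3–10 / 11–30 / >30 | 0–2; 6–10 / 11–50 / >50 | 3–5 (1 → none); 31–50 (3 → 2) |
| Urine WBC per HPF | 6–10 / 11–30 / >30 | 0–5; 6–10 / 11–50 / >50 | 31–50 (3 → 2) |

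**Counts.**

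- Glucose: 2 + 8 + 5 = 15 values.
- Potassium: 2 values.
- Albumin: 5 values in each of 4 strata, 5 × 4 = 20.
- Urine RBC: 3 + 20 = 23 counts.
- Urine WBC: 20 counts.

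The hematology and coagulation cut-offs match. No value is Grade 2 in the protocol and ungraded in the SAP.

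**Gaps within SAP Table 4.** Potassium 3.0–3.1, albumin 3.0–3.4 and urine RBC 3–5 are outside the SAP reference range and have no grade. Note 5 to the table assigns Grade 1 when the laboratory reports RBC as the range 3–10; it does not cover an absolute count of 3, 4 or 5.

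**Effect on treatment emergence.** Only glucose 47–54 crosses the Grade 1/2 line. Take a subject with baseline glucose 55–64. That is Grade 1 in both tables, and it is admissible because glucose is not among the analytes that Note 1 requires to be within range. A post-dose value of 47–54 is then a Grade 2 TEAE under the protocol. Under SAP section 9.6 it is still Grade 1, so not treatment-emergent, and the note to SAP Table 23 shows it as ONR (outside normal range).

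At the other end, a subject who starts at 70 or above and falls to 65–69 has a Grade 1 TEAE under the protocol but lies inside the SAP reference range, so by that range is not even ONR.

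**Overlaps with the reference range.** In SAP Table 4 the finding of few bacteria on urine microscopy is both reference and Grade 1. Female creatinine has reference range 0.57–1.00 and Grade 1 of 0.58–1.50. In steps of 0.01 mg/dL the reference range holds (1.00 − 0.57)/0.01 + 1 = 44 values, of which (1.00 − 0.58)/0.01 + 1 = 43 also meet Grade 1. The protocol has the same Grade 1 cell for female creatinine, so this is a shared defect and not a difference between the documents.

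**The case against.** **Version lag.** The SAP was written against protocol v3.0, which is not among the documents, so Table 4 may have been a faithful copy when written. That could explain the differences and cannot be ruled out. It does not remove them, because the documents contain no addendum that reconciles the tables. Nor does it make the gaps inside SAP Table 4 workable.

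**Redundancy.** SAP sections 4.5.1 and 9.3 send TEAE definitions and severity back to protocol section 9.2. In the glucose example the Grade 2 event would still appear in the TEAE tables, in Table 22 if non-serious, and in Listing 8. The raw value would appear in Listing 9 and in the summaries of Tables 31–32. This stands: information is not lost, and ungraded out-of-range values are still listed as ONR. What remains is that the displays contradict each other.

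**The ONR reading.** The note to Table 23 speaks of results not worse than baseline, and 47–54 is numerically worse than 55–64. Reading worse as a change of grade is an inference, but it follows SAP section 9.6, which defines treatment emergence by grade.

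**Urine counts.** The laboratory's reporting format is not stated, so the urine figures apply if absolute counts are reported. That caveat stands.

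**Weight.** No primary PK endpoint, analysis population or hypothesis test is touched. That is accepted and limits the seriousness.

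**Conclusion.** The concern holds. Five analytes are graded differently in the two documents, and three rows of SAP Table 4 leave out-of-range values ungraded. The differences cover 15 glucose values, 2 potassium values, 5 albumin values in each of 4 strata, 23 urine RBC counts and 20 urine WBC counts. Of these, the 8 glucose values from 47 to 54 cross the line that decides whether a pre-existing Grade 1 value has become treatment-emergent.

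The consequence is contradictory severity in Tables 29–30 and 47–48 and in the abnormal-result listings. With 20 subjects, one reclassified subject moves a percentage by 1/20 = 5 points. The halting rule is graded under the protocol and is not affected.

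The counts assume glucose in whole mg/dL, potassium and albumin to one decimal, and urine microscopy as absolute counts. How many subjects will fall in the affected bands cannot be known from the documents. This should be corrected before analysis; it does not threaten the primary PK results.

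**What to change.** Before data lock, the sponsor should reconcile SAP Table 4 with protocol Appendix B Table 3 so that both use one agreed set of grading cut-offs, and derive every laboratory severity table from it. In doing so:

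- close the potassium, albumin and urine RBC gaps;
- resolve the overlaps with the reference range (few bacteria in urine, female creatinine Grade 1);
- keep the SAP reference-range column, which the ONR and abnormal low/high displays need;
- update the SAP's references to protocol v3.0.

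Which cut-offs to adopt is a clinical decision for the sponsor, and none is proposed here.

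The cost is a SAP addendum, which SAP section 15 allows before final data lock, and a short protocol clarification if a protocol cell changes. No new data are needed.

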#### Nonclinical Assessment of Safety

Extensive nonclinical safety core battery studies have been conducted in the rat and the Beagle dog to evaluate the effects of apramycin on organ systems (IB 2021).

Repeat-dose toxicity studies identified the kidneys as the main target organ of toxicity. Nephrotoxicity manifested as increases in plasma creatinine and BUN, and histopathological changes in the kidney, primarily tubular necrosis with or without regeneration. Nephrotoxicity was exposure-related, with a lower incidence and severity after the recovery period, suggesting potential reversibility. Nephrotoxicity appeared to correlate better with cumulative exposure than with total AUC (0-24) (IB 2021).

Ototoxicity is a known risk of aminoglycosides. A repeat, 16-day dose study in guinea pigs showed that apramycin ototoxicity progressed more gradually than under gentamicin treatment, and cochlear function was partly retained even at high concentrations (430 mg apramycin/kg body weight). "No ototoxic effects were observed in the guinea pig model at the 152 mg/kg/day dose level. This would convert to a human equivalent dose (HED) of 33.3 mg/kg, a single dose exposure of 0.8 mMÅ~h, and a cumulated exposure of 13.7 mMÅ~h, all of which are markedly higher than the nephrotoxic no observed adverse effect levels (NOAELs) in both rats and dogs." (Matt 2012) Recent literature data support the finding that apramycin is of lower ototoxicity than gentamicin (Ishikawa 2019).

Besides nephrotoxicity and ototoxicity, no other noteworthy findings in clinical signs and symptoms were observed. Apramycin showed no effects on the CNS, cardiovascular, or respiratory systems (IB 2021).

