Abnormal safety laboratory values after dosing will be graded for severity per Appendix B, Table 3 and Table 4. Abnormal values within the allowable Grade 1 range per Appendix B noted at screening or baseline will only be considered TEAEs if they deteriorate after study drug dosing to Grade 2 or higher.

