#### 9.2.3 Procedures to be Followed in the Event of Abnormal Laboratory Test Values or Abnormal Clinical Findings

A licensed study clinician (listed on FDA Form 1572) will determine seriousness, severity, and causality of abnormal laboratory values; provide a medical evaluation of TEAEs; and classify TEAEs based upon medical judgment.

Abnormal laboratory values or clinical findings for all enrolled subjects after dosing will be assessed using the toxicity scales in Appendix B. Out of range values and findings noted at screening or baseline, but allowable for enrollment and dosing if within Grade 1, will only be considered TEAEs if their severity increases to Grade 2 or higher. For abnormalities noted from the time of study drug dosing, any Grade 1 or higher laboratory abnormality listed on the toxicity Table 3 in Appendix B will be entered in the database as a TEAE. Safety laboratory results that are reported as TEAEs will be evaluated by the CTU clinician as clinically significant (CS) or not clinically significant (NCS). Abnormal laboratory values, performed as part of HEM, COAG, CHEM, or UA but not listed in this toxicity table will be evaluated by the study clinicians, recorded in the source document and, if clinically significant, considered TEAEs and graded according to the criteria in Section 9.2.1.

Protocol-specific laboratory normal range values are included in the study-specific MOP and toxicity grades for evaluation of TEAEs are included in Appendix B, Table 3.

Gross blood in urine that is confirmed due to menses is not a TEAE (but is for all other reasons).

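### Female creatinine Grade 1 starts at 0.58 mg/dL in both grading tables, inside the normal range, where 1.01 is evidently meant; separately, SAP Table 4 differs from protocol v5.0 on five laboratory parameters

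*SAP*

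**What the plan says.** **Female creatinine.** SAP Table 4 gives, in the order reference range, Grade 1, Grade 2, Grade 3: "Creatinine increase, female – mg/dL 0.57 - 1.00 0.58 - 1.50 1.51 - 3.00 >3.00". Protocol v5.0 Appendix B Table 3, which has no reference column, gives the same grades: "Creatinine increase, female – mg/dL 0.58 – 1.50 1.51 - 3.00 >3.00". The male row in SAP Table 4 is "Creatinine increase, male – mg/dL 0.76 - 1.27 1.28 - 1.90 1.91 - 3.80 >3.80".

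**How the grades are used.** Protocol 8.2.1: "Abnormal safety laboratory values after dosing will be graded for severity per Appendix B". Protocol 9.2.3 makes a graded result an adverse event: "For abnormalities noted from the time of study drug dosing, any Grade 1 or higher laboratory abnormality listed on the toxicity Table 3" is entered as a TEAE. Two sentences exempt a baseline already in Grade 1 until it reaches Grade 2. Section 8.2.1 says "Abnormal values within the allowable Grade 1 range per Appendix B noted at screening or baseline will only be considered TEAEs if they deteriorate" to that level, and section 9.2.3 covers "Out of range values and findings noted at screening or baseline, but allowable for enrollment and dosing if within Grade 1". Note 3 to protocol Table 3, repeated in SAP Table 4, gives the same exemption but ties it only to a value overlapping the Grade 1 range, without requiring that the value be abnormal.

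**How the results are tabulated.** SAP 9.6 sends chemistry grades to Tables 29 and 30. The shell counts every participant with a result in N, has baseline and post-dose rows, and states no filter to abnormal results.

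**Versions.** The SAP is v1.0 of 7 February 2023 and cites protocol v3.0. The protocol supplied is v5.0 of 10 July 2023.

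**The concern.** A creatinine value cannot be both normal and a Grade 1 increase, yet almost the whole female normal range is. Protocol 2.2 states "Repeat-dose toxicity studies identified the kidneys as the main target organ of toxicity", so this is the wrong row in which to carry a wrong bound. Two things could follow from literal use:

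- Programming the printed limits for Tables 29 and 30 without first selecting abnormal results would count women with creatinine 0.58-1.00 as Mild, at baseline and after dosing.
- Under Note 3 read alone, a woman with a normal baseline would already sit in the Grade 1 range, so a true rise to 1.01-1.50 would not be entered as a Grade 1 TEAE.

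The two errors run in opposite directions: false Grade 1 counts in the tables and missing Grade 1 events in the TEAE data.

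A second, independent matter is that SAP Table 4 and protocol v5.0 Table 3 give different limits for five parameters, so the site and the SAP can grade one result differently.

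**Working it through.** **1. Where 0.58 comes from.** Inputs are the two creatinine rows of SAP Table 4.

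| Quantity | Male | Female |
|---|---|---|
| Reference range | 0.76-1.27 | 0.57-1.00 |
| Lower limit + 0.01 | 0.77 | **0.58** (printed) |
| Upper limit + 0.01 | **1.28** (printed) | 1.01 |
| 1.5 × upper limit | 1.905 (printed 1.90) | 1.50 (printed 1.50) |
| 3 × upper limit | 3.81 (printed 3.80) | 3.00 (printed 3.00) |

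The printed 0.58 is reproduced only by stepping up from the lower limit. The other female cut-offs follow the male pattern. Only the start of Grade 1 is out of line, and 1.01 restores it.

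**2. Is it isolated?** SAP Table 4 has 10 hematology + 3 coagulation + 29 chemistry + 2 urine microscopy = 44 numeric rows. Each Grade 1 interval was compared with its reference range, honoring the strict bounds. One row overlaps: female creatinine. Of the 27 rows that grade upward, the other 26 start above their upper limit.

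**3. Size of the overlap, on a 0.01 grid.** The reference range 0.57-1.00 has 44 values, of which 0.58-1.00 (43) are also Grade 1. With 1.01-1.50 (50 values) the overlap is 0. These are grid values, not women.

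**4. The literal Note 3 case.** Take a baseline of 0.70. Under 8.2.1 and 9.2.3 that is normal, so a rise to 1.01-1.50 is a Grade 1 TEAE. Under Note 3 alone it is exempt until 1.51. To show what such a rise means, use the CKD-EPI equation of protocol 8.2.1 for a woman, with no race factor (assumption):

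eGFR = 141 × min(Scr/0.7, 1)^−0.329 × max(Scr/0.7, 1)^−1.209 × 0.993^age × 1.018

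| Assumed age | Scr 0.70 | Scr 1.01 | Scr 1.50 |
|---|---|---|---|
| 18 | 126.5 | 81.2 | 50.3 |
| 30 | 116.3 | 74.6 | 46.3 |
| 45 | 104.6 | 67.2 | 41.6 |

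**5. SAP Table 4 against protocol v5.0 Table 3.** Eight rows differ (albumin has four), covering five parameters.

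| Parameter | Protocol v5.0 | SAP v1.0 | Values graded differently |
|---|---|---|---|
| Potassium, low | G1 3.0-3.4 | G1 3.2-3.4 | 3.0-3.1: 2 |
| Albumin, low | G1 down to 3.0 | G1 down to 3.5 | 3.0-3.4: 5 |
| Fasting glucose, low | G1 55-69, G2 40-54, G3 <40 | G1 47-64, G2 42-46, G3 <42 | 65-69, 47-54, 40-41: 5 + 8 + 2 = 15 |
| Urine RBC/HPF | G1 3-10, G2 11-30, G3 >30 | G1 6-10, G2 11-50, G3 >50 | 3-5, 31-50: 3 + 20 = 23 |
| Urine WBC/HPF | G2 11-30, G3 >30 | G2 11-50, G3 >50 | 31-50: 20 |

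Only glucose 47-54 (8 values) crosses the line between Grade 1 and Grade 2. The SAP limits leave abnormal values with no grade in six rows: potassium 3.0-3.1, the four albumin rows at 3.0-3.4, and urine RBC 3-5. Note 5 to SAP Table 4 closes the RBC gap only if the laboratory reports ranges. In a non-numeric row, SAP urine bacteria, *few* is listed both as normal and as Grade 1.

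**The case against.** The governing text already blocks most of the effect. Protocol 8.2.1 and 9.2.3, SAP 4.5.1 and 9.6, and Listing 9 all speak of grading abnormal results, and the female reference range stands in the same row of SAP Table 4. A footnote defining a denominator does not change which results are graded. The Note 3 reading sets one note against two protocol sections. Note 1 to Table 3 and inclusion criterion 2 also deny creatinine the Grade 1 allowance on which Note 3 rests. Taken literally, 0.58 would bar almost every woman with normal creatinine from enrollment, so the slip should show itself at screening. A rise to 1.01-1.50 would still be counted as abnormal high in Tables 27 and 28, and the eGFR fall would still be summarized. In a 20-subject descriptive study, this argues for calling the error minor.

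Most of that stands, and it is why this is a risk and not a certain misclassification. It does not make the printed number right. The eligibility argument makes 0.58 more plainly wrong, and correct grading then depends on staff and programmers disregarding a printed safety threshold. Protocol Table 3 has no reference column to warn them.

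On the five differences, version lag is the likely cause, and protocol v3.0 is not available to show whether the SAP was right when written. Version lag does not explain the creatinine bound, which is still in protocol v5.0. Aligning the SAP to v5.0 would keep it.

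**Conclusion.** The concern holds. The female creatinine Grade 1 bound is wrong in both documents and should be 1.01. That it is a misprint is an inference, but the male row, the 1.5 and 3 times upper-limit cut-offs and the other 43 rows all support it.

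The possible effect is limited to Grade 1 creatinine counts for women in SAP Tables 29 and 30 and, under the literal Note 3 reading, entry of a rise to 1.01-1.50 as a Grade 1 TEAE. Grade 2 and 3 limits, the laboratory halting rule (Grade 2 or higher), PK, change from baseline, eGFR summaries and Tables 27 and 28 are unaffected. A fall in eGFR has no row in the toxicity table, but protocol 9.2.3 still sends it to the clinician. The eGFR figures are illustrations at assumed ages.

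This should be fixed, on the creatinine bound alone. The five SAP differences are real but secondary. Values left without a grade would still be listed as outside the normal range and counted as abnormal.

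**What to change.** Set female creatinine Grade 1 to 1.01-1.50 mg/dL in protocol Appendix B Table 3 and SAP Table 4. No normal value then falls in Grade 1, so neither literal reading can arise and no rule needs rewording.

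In a SAP addendum, align potassium, albumin, fasting glucose, urine RBC and urine WBC with protocol v5.0, and reconcile the reference column at the same time. Otherwise the v5.0 glucose Grade 1 (55-69) would overlap the SAP reference range (65-99) at 65-69, repeating the creatinine problem. Urine bacteria *few* also needs a single classification. The documents do not settle which reference limits are right; protocol 9.2.3 places the normal ranges in the MOP, so take them from there.

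The cost is one protocol row, which under protocol 14.2 needs IRB approval as an amendment, and one SAP addendum. SAP section 15 allows an addendum only before final data lock. No new data are needed and PK analyses do not change.
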